4.2. Background

In Protocol No. XSMP-201, a Phase 2a clinical trial, Glucagon RTU was evaluated in a dose-seeking study among 12 adults aged 18 to 50 years with T1D. The study was conducted in an inpatient clinical research center setting, and tested doses of 75, 150, and 300 µg. Subjects were

studied on 3 separate occasions using 2 independent injections of glucagon on each study day. All treatments were well tolerated, no SAEs were observed and AEs were generally mild in nature and consisted primarily of pain or a burning sensation at the injection site. Observations of edema and erythema were generally mild and transient. Nausea occurred at the high dose only, in one- third of the patients.

Glucagon injections were made both after an overnight fast and several hours later, following an injection of insulin to mimic the amount they would have taken for a 30-g carbohydrate snack. The study results showed a clear dose response with an initial response observed after 15 to 20 minutes, and the peak time of response after 30 to 45 minutes, both after an overnight fast and following insulin to induce mild hypoglycemia. In all cases, subjects responded to the 150 and 300 µg doses with an increase of plasma glucose of 40 to 100 mg/dL following an overnight fast, and a somewhat smaller increase of 40 to 60 mg/dL following insulin. The 75 µg dose resulted in a smaller rise in glucose (+30 mg/dL) in most subjects, but in no case did the glucose continue to decrease after SC glucagon administration even at that lowest dose. On the basis of these results, a dose of 150 micrograms was selected for a follow-up study for prevention of exercise-induced hypoglycemia.

Protocol No. XSMP-203 was a single-blind, randomized 4-way crossover pilot study involving 15 adult subjects with T1D, ages 18 to 64 years, using continuous subcutaneous insulin infusion (CSII) and wearing a continuous glucose monitor. At 5 minutes prior to 45-minute sessions of moderate aerobic exercise, subjects received a 150-µg dose of Glucagon RTU or performed one of 3 alternate approaches for prevention of hypoglycemia: (1) consumed 20-gm glucose tablets, (2) implemented a 50% reduction in basal rate insulin, or (3) no intervention prior to exercise (ie, untreated control).

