During exercise, plasma glucose increased slightly with Glucagon RTU compared to a decrease with control and insulin reduction, and a greater increase with glucose tablets. Insulin levels were not different among sessions, while glucagon increased with Glucagon RTU. Hypoglycemia (≤ 70 mg/dL (3.89 mmol/L)) was experienced by 6 subjects in the control arm, 5 subjects in the insulin reduction arm, and no subjects using glucose tablets or Glucagon RTU. A total of 5 subjects experienced hyperglycemia (≥ 250 mg/dL) with glucose tablets and 1 with Glucagon RTU.

There were no SAEs reported in the study and no subjects discontinued prematurely. No participant reported nausea during exercise, but 2 participants reported nausea with symptoms of bloating post-exercise after receiving Glucagon RTU.

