8. Questionnaires/Forms will be filled out: Barriers to Physical Activity Diabetes (Type 1) (BAPAD-1), Hypoglycemia Fear Survey (HFS) and Hypoglycemia Confidence Scale (HCS). These questionnaires are only administered at Visit 3/ Treatment 1.
9. The subject will be randomized for this study. (This only occurs at Visit 3/ Treatment 1).
10. Starting at 5 minutes prior to exercise:
 - a. The subject will reduce the basal infusion rate of insulin by 50%.
 - b. Study Medication will be administered based upon randomization assignment.
11. Subject will then complete an exercise session (See [Appendix 1](#)[bookmark99](#)).

 - a. Heart rate will be monitored via the Fitbit Ionic device and Polar Beat H10 heart rate sensor during these exercise sessions.
 - b. During the exercise session, the subject is to drink carbohydrate free liquids only (e.g., Powerade Zero or comparable product) and will be provided with glucose/dextrose tabs to use as needed.
 - c. Per ADA guidelines, if a subject's glucose falls to ≤ 70 mg/dL (3.89 mmol/L) during any exercise session, then the exercise session should be stopped, the subject should rest, and glucose tabs should be taken every 15 minutes until the hypoglycemia is corrected and euglycemia (confirmed by BGM) is maintained. Subjects will be provided with a supply of glucose tabs and instructed to use these rather than other sources of carbohydrate to treat hypoglycemia.

12. Following completion of exercise:
 - a. Basal rate insulin will be returned to the pre-exercise infusion rate.
 - b. PI or delegate will administer Draize Scales for erythema and edema and the Injection Site Discomfort Description and Duration Questionnaire.
13. Before, during and after exercise, venous blood samples (YSI) for glucose measurements will take place at the following time points. Subjects will perform a blood glucose measurement using a BGM as indicated below with a window of ± 2 minutes:
 - a. -15 minutes (both YSI and BGM)
 - b. Time 0 (immediately before exercise) (both)
 - c. 15 minutes (YSI only)
 - d. 30 minutes (both)
 - e. 45 minutes (both, end of exercise)
 - f. 60 minutes (YSI only)
 - g. 75 minutes (both, thirty minutes after completion of exercise)

14. AE assessment.

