APPENDIX 1. EXERCISE**CRC EXERCISE**

Subjects may proceed with exercise if BG is 100-180 mg/dL (5.56 – 10 mmol/L).

Exercise will consist of 45-minute session of moderate intensity aerobic activity (eg, treadmill jogging/brisk walking/cycling, elliptical). Breaks in exercise may be taken to perform study procedures. Each break will be 5 minutes or less with an aggregate break time of no more than 10 minutes.

The same type of aerobic activity will be performed for each exercise session and for the entire duration of each exercise session. The target is for exercise sessions to be initiated at approximately the same clock time during each CRC visit, with a window of ± 1 hour.

The goal is to achieve a target of 80% of maximum calculated heart rate during the session as shown in the following equation:

Recommended exercise goal:

$$\text{Heart Rate} = 0.80 \times (220 - \text{Age in Years})$$

Stopping rule: As long as glucose remains >70 mg/dL, exercise may continue. If the subject's glucose falls to ≤ 70 mg/dL (3.89 mmol/L), the exercise session will be stopped, the subject should rest, and 16g (4 tabs, 4g/tab) of glucose tabs, or per standard of care, should be taken every 15 minutes until hypoglycemia is corrected and euglycemia is maintained.

OUTPATIENT EXERCISE

During the out-patient phase, subjects will be instructed to self-administer Study Medication when the following three conditions are met:

1. The subject plans to perform an aerobic exercise session lasting at least 30 minutes and not more than 75 minutes in duration,
2. The subject plans to exercise continuously at moderate-to-high intensity to achieve a target heart rate of 80% of maximum calculated heart rate, during the session.
3. The subject has a confirmed blood glucose (BGM) of 100-180 mg/dL (5.56–10 mmol/L).

Subjects may perform exercise at any point in the day, but dose themselves for a maximum of one exercise session per day. The requested exercise frequency is an average of 2-3 sessions weekly. An instruction manual for self-administration of study drug will be provided to subjects.

Examples of aerobic exercise qualifying for dosing include powerwalking, hiking, running/jogging, cycling, swimming, cross country skiing, and aerobic fitness classes.

High intensity interval training (HIIT) such as sprinting, volleyball, basketball, hockey, CrossFit, weight lifting, etc. is not eligible for investigational product dosing.

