APPENDIX 4. DRAIZE SCALE

- *Study Personnel Instructions:* The modified Draize Scale as shown in the table below will be used for physical examination/rating of abnormalities at the injection site.
- The injection site should be examined for formation of both erythema and edema and results recorded in the Case Report Form. Evaluations of the injection site should be performed at 10 ± 5 and 60 ± 5 minutes after the completion of the exercise session

Erythema Formation		Edema Formation	
Description	Score	Description	Score
No erythema	0	No edema	0
Very slight erythema Barely perceptible	1	Very slight edema Barely perceptible	1
Well defined erythema	2	Slight edema (edges of area well defined by definite raising)	2
Moderate erythema	3	Moderate edema Raised approx. 1 mm	3
Severe erythema Beet redness to slight eschar formation	4	Severe edema Raised more than 1 mm and beyond exposure area	4

Source: Guidance for Industry, Skin Irritation and Sensitization Testing of Generic Transdermal Drug Products. US Department of Health and Human Services Food and Drug Administration Center for Drug Evaluation and Research (CDER). December 1999. Appendix A.

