APPENDIX 6. INJECTION SITE DISCOMFORT DESCRIPTION AND DURATION QUESTIONNAIRE

Study Personnel Instructions: Question 1a should be completed by the subject after injection of study drug and when the exercise is completed. Any subject reporting discomfort other than “none,” should complete Question 1b at the same time. All subjects should also answer Question 1c at the end of the visit (90 ±5 mins post-injection). The goal is for the subject to report the qualitative nature and duration of discomfort, if any, associated with injection of study drug, ignoring any transient pain associated with needle insertion.

Note: If a subject is unable to physically complete the questionnaire, the subject will provide verbal responses, which will be recorded on the questionnaire by study staff. Documentation will be provided on each completed questionnaire as to who completed the form (subject or staff).

Subject Instructions: Please answer question 1a and, if applicable to you, questions 1b and 1c. In answering these questions, you should ignore any pain from insertion of the needle. **Please complete question 1c before leaving the clinic.**

1a. How would you describe any discomfort you felt from the study drug? (Check all that apply):

- None (Please ignore question 1b.)
- Pain (e.g., throbbing, soreness, muscle ache)
- Itching
- Tingling, twitching or numbness
- Irritation (e.g., burning, stinging)

Other or additional comments: _____

1b. About how long did the discomfort last after the injection? (Check one):

- Less than 1 minute
- 1-2 minutes
- 3-5 minutes
- 6-9 minutes
- at least 10 minutes

1c. In total, how long did the discomfort last after the injection? (Please enter a number below):

_____ Minute

Glucagon RTU (Glucagon Injection)
Protocol XSMP-204

Version 4.0

Source: Downie WW, Leatham PA, Rhind VM, Wright V, Branco JA, Anderson JA. Studies with pain rating scales. *Ann Rheum Dis.* 1978;37:378–381.

Document Approvals
Approved Date: 6/20/2019

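### The Draize skin exams are timed from the end of exercise, so the second falls after the stated end of the visit and time since injection varies when a session is stopped early

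*Protocol*

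**What the plan says.** - Protocol Appendix 4 sets the two skin exams relative to exercise: "Evaluations of the injection site should be performed at 10 ± 5 and 60 ± 5 minutes after the completion of the exercise session".
- Protocol Appendix 6 sets the end of the same visit relative to injection: "All subjects should also answer Question 1c at the end of the visit (90 ±5 mins post-injection"). It tells the subject: "Please complete question 1c before leaving the clinic".
- Protocol Section 10.3 schedules the insulin reduction and the injection together: "Starting at 5 minutes prior to exercise". It lists the Draize scales after exercise without clock times, and its last glucose sample is at 75 minutes from the start of exercise.
- Protocol Appendix 1 gives the session length, "Exercise will consist of 45-minute session of moderate intensity aerobic activity", and allows breaks: "Each break will be 5 minutes or less with an aggregate break time of no more than 10 minutes".
- Section 10.3 and Appendix 1 stop the session if glucose falls to ≤70 mg/dL. Neither they nor Appendix 4 say whether a stopped session counts as completed for timing the exams.
- SAP Section 4.3.9 summarizes erythema and edema descriptively in the CRC phase, Safety population. It plans no treatment test and no account of time since injection.

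**The concern.** There are two separate problems, and they arise in different sessions.

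In a full-length session the appendices cannot both be followed. Staff must do the second exam outside its window, omit it, or keep the subject past the stated end of the visit, and sites may choose differently.

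In a session stopped for low glucose, the time from injection to exam depends on the event the drug is meant to prevent. Each subject receives both treatments, so the natural comparison is of two injection sites at the same age. An anchor tied to exercise duration does not guarantee that.

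At stake is local tolerability. The Draize scale is the study's only dedicated staff grading of erythema and edema, and it is done only at Visits 3 and 4.

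**Working it through.** **Inputs.** Injection lead L = 5 min (Section 10.3). Full exercise duration D = 45 min, or 55 min elapsed if all 10 minutes of breaks are added (Appendix 1; SAP Section 2.4 excludes breaks from the 45 minutes). Exam offsets O = 10 and 60 min, each ± 5 (Appendix 4). Visit end = 90 ± 5, that is 85 to 95 min post-injection (Appendix 6).

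**The protocol's own check.** The last glucose sample is described as 30 minutes after exercise ends: 45 + 30 = 75 min from the start, which agrees. Post-injection this is 5 + 75 = 80 min, which fits a visit ending at 85 to 95. The 90-minute figure is therefore coherent with the sampling schedule.

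**Formula.** Minutes post-injection = L + D + O.

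| Case | Exam 1 | Exam 2 | Exam 2 minus 90 |
|---|---|---|---|
| Full session, no breaks | 5 + 45 + 10 = 60 (55–65) | 5 + 45 + 60 = 110 (105–115) | +20 |
| Full session, 10 min breaks | 5 + 55 + 10 = 70 (65–75) | 5 + 55 + 60 = 120 (115–125) | +30 |
| Injection at time 0, no breaks | 0 + 45 + 10 = 55 (50–60) | 0 + 45 + 60 = 105 (100–110) | +15 |
| Stopped at 30 min | 5 + 30 + 10 = 45 (40–50) | 5 + 30 + 60 = 95 (90–100) | +5 |
| Stopped at 15 min | 5 + 15 + 10 = 30 (25–35) | 5 + 15 + 60 = 80 (75–85) | −10 |

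The 15- and 30-minute stops are the scheduled glucose checks before the end of exercise. The stopped rows assume that stopping counts as completion.

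**Full sessions.** Without breaks, the second exam is 105 − 95 = 10 to 115 − 85 = 30 minutes after the stated visit end. Even with injection at time 0 the windows miss by 100 − 95 = 5 minutes. The second exam is nominally late whenever 5 + D + 60 > 90, that is D > 25 minutes.

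**Stopped sessions.** Both exams move earlier by 45 − 30 = 15 or 45 − 15 = 30 minutes, and the second comes back toward or inside the visit.

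**How unequal the timing could be (illustration only).** In XSMP-203, with 15 subjects, Section 4.2 reports hypoglycemia in "5 subjects in the insulin reduction arm, and no subjects using glucose tablets or Glucagon RTU". Assume those rates carry over and that every event stops exercise. The average placebo exam is then earlier by 15 × 5/15 = 5 minutes (stops at 30) or 30 × 5/15 = 10 minutes (stops at 15). With the exact 95% interval for 5/15 (0.118 to 0.616) and glucagon held at 0, the range is 15 × 0.118 = 1.8 to 30 × 0.616 = 18.5 minutes. This is a difference in exam timing, not in Draize score.

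**The case against.** The strongest reply is that the 90 ± 5 minutes only times Question 1c. Section 10.3 sets no discharge time, and the subject is told only to answer 1c before leaving. Staff could collect 1c at 90 minutes and keep the subject for the exam. A reader might infer that the second exam will be missed; the documents do not support that. What stands is that Appendix 6 calls that time the end of the visit while Appendix 4 schedules a later procedure.

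A reader might also infer that the timing biases the study so that glucagon looks milder than it is. That would follow only if reactions were still fading when the exams take place. The documents give no time course for erythema or edema, only "Observations of edema and erythema were generally mild and transient". The XSMP-203 insulin-reduction arm is not described as receiving an injection, and its events are not placed during exercise. Nor does the questionnaire's at-least-10-minutes category show that the first exam comes too late: it is open-ended and concerns discomfort, not skin signs.

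It is also fair that the two problems do not compound, since an early stop pulls the second exam back. The data are only summarized, and skin reactions can also be reported and graded as adverse events. None of this supplies a rule for stopped sessions.

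**Conclusion.** The contradiction between Appendix 4 and Appendix 6 is certain for any full session: the second exam is nominally 20 minutes after the stated visit end (30 with full breaks), with no overlap of windows. This rests only on the protocol's own times.

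The dependence of exam timing on early stopping follows if stopping counts as completion, which the protocol leaves open. The shift is then 15 or 30 minutes for stops at the 30- or 15-minute check. That placebo sessions stop more often is an expectation drawn from XSMP-203. Distortion of the glucagon-versus-placebo summary is therefore a risk, neither demonstrated nor quantifiable from the documents.

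The consequence is confined to descriptive CRC-phase local-tolerability data. The primary and secondary endpoints and the sample size are untouched. The change is still worth making because it is cheap.

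**What to change.** In Appendix 4 and Section 10.3.1, time both exams from injection, identically for completed and stopped sessions and without interrupting exercise. For example:

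- First exam at 60 ± 5 minutes post-injection, which equals the present first exam in a full session without breaks (5 + 45 + 10 = 60). With full breaks, exercise ends at 5 + 55 = 60 minutes, so the exam can still be done at 60 to 65.
- Second exam at 90 ± 5 minutes, together with Question 1c.

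Alternatively, keep a later second exam at a fixed post-injection time and move the Appendix 6 visit end to match. Keeping 110 ± 5 would need a visit end of at least 115 minutes.

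Record the actual minutes since injection on the CRF and show them in the SAP's Draize summary. Dosing date and time are already listed under the SAP section on study drug administration, so what is needed is the clock time of each exam.

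The cost is appendix wording and a CRF time field, with the same staff and number of exams. The downside is small: the second exam comes earlier than now, or the visit is longer, and the times would differ from any earlier study that used post-exercise timing.

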APPENDIX 5. HYPOGLYCEMIC CONFIDENCE SCALE

How confident are you that you can stay safe from serious problems with hypoglycemia:	Not Confident At All	A Little Confident	Moderately Confident	Very Confident
1. When you are exercising?				
2. When you are asleep?				
3. When you are driving?				
4. When you are in social situations?				
5. When you are alone?				

In general, how confident are you that you can:	Not Confident At All	A Little Confident	Moderately Confident	Very Confident
6. Avoid serious problems due to hypoglycemia?				
7. Catch and respond to hypoglycemia before your blood sugars get too low?				
8. Continue to do things you really want to do in your life, despite the risks of hypoglycemia?				

9. If you have a spouse or partner: What is your best guess about how confident your spouse or partner feels about your ability to avoid serious problems due to hypoglycemia?				
--	--	--	--	--

APPENDIX 6. INJECTION SITE DISCOMFORT DESCRIPTION AND DURATION QUESTIONNAIRE

Study Personnel Instructions: Question 1a should be completed by the subject after injection of study drug and when the exercise is completed. Any subject reporting discomfort other than “none,” should complete Question 1b at the same time. All subjects should also answer Question 1c at the end of the visit (90 ±5 mins post-injection). The goal is for the subject to report the qualitative nature and duration of discomfort, if any, associated with injection of study drug, ignoring any transient pain associated with needle insertion.

Note: If a subject is unable to physically complete the questionnaire, the subject will provide verbal responses, which will be recorded on the questionnaire by study staff. Documentation will be provided on each completed questionnaire as to who completed the form (subject or staff).

Subject Instructions: Please answer question 1a and, if applicable to you, questions 1b and 1c. In answering these questions, you should ignore any pain from insertion of the needle. **Please complete question 1c before leaving the clinic.**

1a. How would you describe any discomfort you felt from the study drug? (Check all that apply):

- None (Please ignore question 1b.)
- Pain (e.g., throbbing, soreness, muscle ache)
- Itching
- Tingling, twitching or numbness
- Irritation (e.g., burning, stinging)

Other or additional comments: _____

1b. About how long did the discomfort last after the injection? (Check one):

- Less than 1 minute
- 1-2 minutes
- 3-5 minutes
- 6-9 minutes
- at least 10 minutes

1c. In total, how long did the discomfort last after the injection? (Please enter a number below):

_____ Minute

Glucagon RTU (Glucagon Injection)
Protocol XSMP-204

Version 4.0

Source: Downie WW, Leatham PA, Rhind VM, Wright V, Branco JA, Anderson JA. Studies with pain rating scales. *Ann Rheum Dis.* 1978;37:378–381.

Document Approvals
Approved Date: 6/20/2019

**REVISION HISTORY**

Version	Date	Author	Reasons
1.0	05 Dec 2019	[name]	Initial version

Approved

## LIST OF ABBREVIATIONS

Abbreviation or special term	Explanation
AE	Adverse event
ANCOVA	Analysis of Covariance
ANOVA	Analysis of Variance
AOC	Area Over the Curve
AUC 0-xh	Area under the plasma concentration vs time curve from time 0 to X hours post-dose (where x=1 hour, 2 hours, 4 hours post-dose). AUC 0-xh is estimated using the trapezoidal method.
BGM	Blood Glucose Monitoring
BGMT	Blood Glucose Measurement
BMI	Body Mass Index
CBP	Childbearing potential
CGM	Continuous Glucose Monitoring
CI	Confidence Interval
CRF	Case Report Form
CRO	Contract Research Organization
CTCAE	Common Terminology Criteria for Adverse Events
CV%	Coefficient of Variation expressed as a percentage
ECG	Electrocardiogram
eCRF	Electronic Case Report Form
EDC	Electronic Data Capture
ER	Extended Analysis
FDA	United States Food and Drug Administration
GCP	Good Clinical Practice
HR	Heart Rate
ICF	Informed Consent Form
ICH	International Council for Harmonization
IG	Interstitial Glucose
IMP	Investigational Medicinal Product
ITT	Intent-to-Treat
MedDRA	Medical Dictionary for Regulatory Activities

Abbreviation or special term	Explanation
PP	Per Protocol
PROs	Patient Reported Outcomes
PT	Preferred Term
QTc	Corrected QT interval
QTcF	QT interval corrected for heart rate using Fridericia's method
RBC	Red Blood Cell
RTY	Ready To Use
SAE	Serious Adverse event
SAP	Statistical Analysis Plan
SBP	Systolic Blood Pressure
SD	Standard Deviation
SOC	System Organ Class
TEAE	Treatment-Emergent Adverse Event
WBC	White Blood Cell
WHO	World Health Organization
YSI	Yellow Springs Instrument

## INTRODUCTION

The purpose of this statistical analysis plan (SAP) is to provide the details of the planned statistical analyses that were outlined within the protocol for the study “A Phase 2 Randomized, Placebo-Controlled, Double-Blind, Parallel Study to Evaluate Glucagon Ready-to-Use (RTU) (Glucagon Injection) Compared to Standard of Care for the Prevention of Exercise-Induced Hypoglycemia During Regular Aerobic Exercise in Adults with Type 1 Diabetes”, XSMP-204, version 4.0 dated 20 June 2019. The SAP will further define and expand those analyses. The SAP will take precedence over the protocol.

